11.1 Sample Size Estimation

Estimation of sample size is based on the demonstration of improved sleep efficiency (SE) in short-term insomnia patients treated with Neurexan® as assessed by polysomnography. The standard deviation (SD) of SE is estimated at 10%. With $\alpha=5\%$, two-sided and an expected mean difference of 6.7% between patients treated with Neurexan® and Placebo, a power of 80% is achieved with 72 patients. Expecting a dropout rate of 10%, the total number of patients needed is 80.

11.2 Randomization

Patients eligible for treatment will be randomized to one of two treatment arms according to a computer-generated randomization plan in a ratio of 1:1 and stratification by sex. Placebo tablets will be identical in appearance, packaging and labelling to Neurexan®. The randomization schedule will be 'blocked' to avoid temporal bias.

Patients' allocation to treatment will take place after completion of all baseline assessments prior to beginning of trial treatment.

The randomization list will be generated according to the appropriate Standard Operating Procedures (SOPs). Sealed copies will be stored by the Trial Statistician and the Sponsor/ Drug Safety and will not be opened prior to termination of the double-blinded trial, i.e., after data base lock.

11.3 Statistical Planning

A detailed methodology for summary and statistical analysis of the data collected in this trial will be documented in a Statistical Analysis Plan (SAP). This has to be finalized at the latest prior to database lock. This document may modify the plans outlined in the protocol; however, any major modification of the primary endpoint definition and/or its analysis would also be reflected in a protocol amendment to be submitted to the Competent Authorities and Independent Ethics Committee for endorsement.

All programming of tables, figures, listings and statistical analyses will be performed using the statistical software package SAS® version 9.4 or higher.

The statistical planning and evaluation of the trial will be carried out by a qualified biostatistician in accordance with the ICH guidelines and adequate biostatistical SOPs.

Definition of Baseline

The last available information at or prior to Baseline 2/ Day 0 collected before randomization and subsequent first IMP intake will be defined as baseline value. For PSG derived parameters the baseline is defined as the night from Day -1 to Day 0 (Baseline 2).

Subgroup Analyses

The following subgroups will be defined:

- Age
- Sex (female/ male)
- Neurexan® responder vs. non-responder
- Duration of short-term insomnia (≤ 1 month, > 1 month)
- Cortisol response influenced by hormonal contraceptives

Other subgroups may be specified in the SAP or during the Blind Data Review Meeting (BDRM).

Descriptive Analyses

All variables will be described by treatment group using descriptive statistics.

For continuous variables the number of observations (n), arithmetic mean, standard deviation (SD), minimum, median, 25%- 75%-quantile, maximum, 95% confidence interval (CI) (2-sided), and the number of missing data will be presented.

For categorical variables n, frequency and percentage, 95% CI (where applicable), and number of missing data will be presented.

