
EEG stress response:
 
○ Changes in time course of EEG vigilance fluctuations during wakefulness assessed by VIGALL version 2.1 (validated with the Multiple Sleep Latency Test (MSLT) by (Olbrich, Pawlowski et al. 2015) at Visit 1 compared to Baseline 1○ Changes in EEG asymmetry index at Visit 1 compared to Baseline 1○ Regional changes in spectral characteristics of EEG using relative power in delta-theta-alpha-beta frequency ranges at Visit 1 compared to Baseline 1.		

• Stress questionnaires Changes in subjective stress levels compared to Baseline 1 as assessed by
• Subclinical Stress Symptom Questionnaire-25 (SSQ-25) at Follow-Up Visit• Primary Appraisal Secondary Appraisal (PASA) at Visit 1• Perceived Stress Scale-10 (PSS-10) at Follow-Up Visit• Continuous (over the whole trial period) daily stress assessment using AMS-ePRO® functionality and EMAs.		

Further secondary objectives are to assess correlations between:
 
• Changes in sleep parameters, stress parameters, and daytime performance• Changes in sleep parameters, stress parameters, and inflammatory parameters.		

Methodology, Trial Design Randomized, double-blind, placebo-controlled exploratory monocentric clinical trial
		

Number of Patients (Planned): Estimation of sample size is based on the demonstration of improved sleep efficiency (SE) in short-term insomnia patients treated with Neurexan® as assessed by polysomnography. The standard deviation (SD) of SE is estimated at 10%. With $\alpha= 5\%$, two-sided and an expected mean difference of 6.7% between patients treated with Neurexan® and Placebo, a power of 80% is achieved with 72 patients. Expecting a dropout rate of 10%, the total number of patients needed is 80.
		

Patients will be randomly assigned to treatment group Neurexan® or Placebo with a 1:1 allocation and stratification by sex.
		

Sponsor: Biologische Heilmittel Heel GmbH	Name of Medical Product: Neurexan® tablets	Active Ingredient(s): Homeopathic preparation, containing herbal and mineral ingredients as described in the Clinical Trial Protocol
EudraCT number: 2022-003565-38		Indication: Short-Term Insomnia
Diagnosis and Inclusion Criteria:		
The patients have to meet all of the following inclusion criteria at Screening Visit:		

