4.2 Secondary Objectives and Endpoints

The secondary objectives are to assess further PSG-based objective as well as subjective sleep parameters, daytime performance and stress processing in patients with short-term insomnia treated daily with Neurexan® compared to Placebo.

Secondary endpoints are described in the following.

Sleep Pattern by

- Further objective sleep parameters revealed by polysomnography (PSG)
To be assessed as change at Visit 2 compared to Baseline 2
 - Sleep Onset Latency (SOL): changes in SOL compared to Baseline 2
 - Wake After Sleep Onset (WASO): changes in WASO compared to Baseline 2
 - Total Sleep Time (TST): changes in TST compared to Baseline 2
 - Number of awakenings (NWAK): changes in NWAK compared to Baseline 2
 - Number of arousals during (Arousal Index; ArI) changes in Arousal Index compared to Baseline 2
 - Latencies to sleeping stages S1, S2, S3, and Rapid Eye Movement (REM): changes in these latencies compared to Baseline 2.
- Objective in-home assessment of sleep pattern revealed by actigraphy (24/7)
 - A portable device, i.e., an actigraphy watch will be used to continuously monitor movement information over the whole clinical trial duration for actimetric sleep–wake detection to investigate habitual sleep–wake patterns and daily activity.
- Subjective sleep pattern assessed using sleep questionnaires and sleep diary (adapted from Deutsche Gesellschaft für Schlafforschung und Schlafmedizin, DGSM), to be recorded on AMS-ePRO®
 - Insomnia Severity Index (ISI): changes in ISI at Visit 1 compared to Baseline 1.
 - Pittsburgh Sleep Quality Index (PSQI): changes in PSQI at Follow-Up Visit compared to Baseline 1.
 - Sleep diary parameters: changes in subjective SE, SOL, WASO, TST, and NWAK compared to baseline.

Daytime Performance by

- Resting state EEG:
 - Changes in time course of EEG vigilance fluctuations during wakefulness assessed by Vigilance Algorithm Leipzig (VIGALL) version 2.1 (validated with the Multiple Sleep Latency Test (MSLT) by (Olbrich, Pawlowski et al. 2015) at Visit 1 compared to Baseline 1
 - Changes in EEG asymmetry index at Visit 1 compared to Baseline 1
 - Regional changes in spectral characteristics of EEG using relative power in delta-theta-alpha-beta frequency ranges at Visit 1 compared to Baseline 1
- Resting state heart rate (HR) and heart rate variability (HRV) and electrodermal activity (EDA) at Visit 1 compared to Baseline 1

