- Questionnaires: Epworth Sleepiness Scale (ESS), Würzburg Fatigue Inventory (WEIMuS) and Beck's Depression Inventory-II (BDI-II) at Visit 1 compared to Baseline 1, and Quality of Life (QoL) by QoL questionnaire Short Form-36 version 2.0 (SF-36v2) and Beck's Anxiety Inventory (BAI) at Follow-Up Visit compared to Baseline 1
- Neuropsychological tests assessing general cognitive functioning, alertness, vigilance, and sustained attention: three subtests from electronic Tests of Attentional Performance (TAP) test battery at Visit 1 compared to Baseline 1.

Stress Processing

Given the reported HPA axis dysregulation in the form of an altered cortisol secretion pattern in insomnia patients, a secondary outcome is to demonstrate changes in decreased resting state stress parameters in saliva as well as stress reactivity to physiological challenge using the Cold Pressor Test (CPT) in terms of changes in serum levels of cortisol in short-term insomnia patients treated with Neurexan®.

- Resting state stress response by
 - Changes in stress biomarkers in saliva compared to baseline
 - Cortisol
 - Alpha-amylase
 - Dehydroepiandrosterone sulfate (DHEA-S)
 - Time course of stress biomarkers release synchronized to the awakening time (5 time points after awakening: 0 minutes, 15 minutes, 30 minutes, 45 minutes, 60 minutes for the assessment of Cortisol Awakening Response (CAR))
 - Diurnal profile of stress biomarkers by collecting saliva samples at 3-hourly intervals over 12 hours (4 time points) synchronized to the awakening time.
- Stress response induced by CPT
 - Changes in subjective pain rating and pain tolerance at Visit 1 compared to Baseline 1

Blood sampling

- Changes in the cortisol time course: Visit 1 before CPT, 20 minutes, and 50 minutes after CPT compared to Baseline 1
- Changes in dehydroepiandrosterone sulfate (DHEA-S) time course: Visit 1 before CPT, 20 minutes, and 50 minutes after CPT; Visit 1 compared to Baseline 1
- Changes in the time course of adrenalin, noradrenalin and the inflammatory response (IL-6 and TNF- α): Visit 1 before CPT, 20 minutes, and 50 minutes after CPT compared to Baseline 1.

Autonomic stress response:

- Changes in heart rate and associated HRV measures, electrodermal activity (EDA); Visit 1 compared to Baseline 1.

EEG stress response:

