- Changes in time course of EEG vigilance fluctuations during wakefulness assessed by VIGALL version 2.1 (validated with the Multiple Sleep Latency Test (MSLT) by (Olbrich, Pawlowski et al. 2015) at Visit 1 compared to Baseline 1
- Changes in EEG asymmetry index at Visit 1 compared to Baseline 1
- Regional changes in spectral characteristics of EEG using relative power indices in delta-theta-alpha-beta frequency ranges at Visit 1 compared to Baseline 1.

• Stress questionnaires

Changes in subjective stress levels compared to Baseline 1 as assessed by

- Subclinical Stress Symptom Questionnaire-25 (SSQ-25) at Follow-Up Visit
- Primary Appraisal Secondary Appraisal (PASA) at Visit 1
- Perceived Stress Scale-10 (PSS-10) at Follow-Up Visit

- Continuous (over the whole trial period) daily stress assessment using AMS-ePRO® functionality and Ecological Momentary Assessments (EMAs).

Further secondary objectives are to assess correlations between:

- Changes in sleep parameters, stress parameters, and daytime performance
- Changes in sleep parameters, stress parameters, and inflammatory parameters

5. Trial Design

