- Complete sleep diary and stress assessment (in **AMS-ePRO®**).

At **Baseline 2** (Day -1 to Day 0) patients will stay at the site for a second night for PSG. After awakening (Day 0) resting state stress parameters in saliva are to be collected (at 5 time points). Patients will be randomly assigned to treatment group Neurexan® or Placebo with a 1:1 allocation and stratification by sex.

The following procedures will be performed:

- Urine collection for test on drugs in the evening at Day -1 (section 9.1.11)
- Breath alcohol test in the evening at Day -1 (section 9.1.11)
- Baseline 2 PSG night to measure primary, i.e., SE and secondary endpoints, i.e., SOL, WASO, TST, NWAK, and ARI during sleep in the night between Day -1 and Day 0 (section 9.1.1)
- Collection of 0.5 to 1 ml saliva to measure cortisol, DHEA-S and alpha-amylase at awakening (0 minutes), and at 15 minutes, 30 minutes, 45 minutes, 60 minutes after awakening at Day 0 (section 9.1.2)
- Adverse events at Day -1 and Day 0 (section 9.2.1)
- Changes in concomitant medication at Day -1 and Day 0
- Randomization to treatment group at Day 0 (section 11.2)
- Distribution of IMP and instruction regarding use of IMP at Day 0
- Starting IMP treatment after having performed all Baseline 2 assessments at midday Day 0 (section 7.1)
- Complete sleep diary and stress assessment (in **AMS**-ePRO®).

Patients will continue to take their trial treatment for 14 consecutive days (Day 0 - Day 13).

At **Visit 1** (Day 12 to Day 13; +2 days) patients return to the trial site for another PSG adaptation night. A urine and breath alcohol test will be conducted on drugs and alcohol, respectively. After awakening (Day 13) resting state stress parameters in saliva are to be collected (at 5 time points) and every 3-hours (at 4 time points). In the course of the morning, patients will perform neuropsychological tests from the TAP battery. An rsEEG and measurement of resting heart rate and HRV and EDA will be performed at approximately 15 minutes prior CPT. Around 12:00 at Day 13 a CPT will be performed, blood samples will be collected (before CPT and 20 minutes and 50 minutes after CPT) and patients will complete a subjective pain and stress rating. During CPT an EEG will be performed and heart rate and HRV will be measured. Additionally, patients will complete questionnaires on sleep, stress and quality of life on paper (BDI-II, WEIMuS) and on **AMS**-ePRO® (ESS, ISI, PASA).

The following procedures will be performed:

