9.1.2 Resting State Stress Response

Resting state stress response will be assessed based on the stress biomarkers cortisol, alpha-amylase and dehydroepiandrosterone sulfate (DHEA-S) in saliva samples.

Around 0.5 to 1 ml of saliva are to be collected at each of 5 time points starting immediately after awakening from PSG adaptation nights (Baseline 1/ Day -1 and Visit 1/ Day 13) and PSG nights (Baseline 2/ Day 0 and Visit 2/ Day 14) followed by sampling at 15 minutes, 30 minutes, 45 minutes and 60 minutes after awakening for the assessment of Cortisol Awakening Response (CAR).

To assess a diurnal profile of stress markers 4 additional saliva samples (around 0.5 to 1 ml/ sample) are to be collected at 4 time points at 3-hourly intervals over 12 hours at Baseline 1/ Day -1 and Visit 1/ Day 13 (Table 4).

Table 4: Resting state saliva sampling

Cortisol Awakening Response					Diurnal Profile*			
After awakening	+15 min	+30 min	+45 min	+60 min	+3 h	+6 h	+9 h	+12 h
X	X	X	X	X	X	X	X	X

*Only at Baseline 1 and Visit 1.

Saliva samples are collected in 2 ml SaliCap sampling tubes (TECAN/ IBL International, Hamburg, Germany, ref. no. RE69985) using short drinking straws. One sample of 0.5 to 1 ml saliva is sufficient to analyze cortisol, alpha-amylase and DHEA-S.

After instruction by the site personnel, samples are collected independently by each trial participant. Salivary samples are stored frozen at -80°C (+/- 10°C fluctuation) for interim storage (approximately 3 months) at the biobank of the local laboratory of the investigational site (Institut für Klinische Chemie und Laboratoriumsdiagnostik, IKCL, Jena University Hospital) before shipping to the saliva biomarker laboratory.

Stress parameter levels in saliva will be analyzed at Dresden LabService GmbH, Dresden, Germany, using commercial immunoassays from IBL International, Hamburg, Germany (i.e., Cortisol Saliva Luminescence ImmunoAssay (CLIA); and DHEA-S Saliva Enzyme-Linked Immunosorbent Assay (ELISA) following manufacturer's instructions. Saliva alpha-amylase will be analyzed following the method of Rohleider and colleagues (Rohleider, Nater et al. 2004).

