9.1.9 Sleep Diary

After patients have given their informed consent, they will receive access to an electronic sleep diary (adapted from DGSM - Deutsche Gesellschaft für Schlafforschung und Schlafmedizin, on **AMS-ePRO®**), which they are asked to complete every day starting at Screening Visit (Day -28 to -8) in the evening until End of Trial (Follow-up Visit/ Day 28). Beside subjective sleep parameters patients will also report their daily intake of IMP, adverse events and concomitant medication, if any.

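### The last-value-before-randomisation baseline contradicts section 4.2 for daily stress, mismatches the Visit 1 saliva awakening samples, and read literally gives the sleep diary one sleep-lab entry

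*Protocol*

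**What the plan says.** Section 11.3 (Definition of Baseline) gives one general rule: "The last available information at or prior to Baseline 2/ Day 0 collected before randomization and subsequent first IMP intake". Its only exception is PSG, for which baseline is the night from Day -1 to Day 0. Section 11.4.2 then uses the baseline value as ANCOVA covariate for continuous secondary variables.

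The three measures concerned are specified as follows.

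- **Daily stress (EMA).** Section 4.2 opens its stress list with "Changes in subjective stress levels compared to Baseline 1 as assessed by". The last item in that list, as in the synopsis, is the "daily stress assessment using AMS-ePRO® functionality and EMAs". Under Baseline 2, section 8.1 also lists "Complete sleep diary and stress assessment".
- **Saliva.** The endpoint in section 4.2 is "Changes in stress biomarkers in saliva compared to baseline", with no visit named. Section 9.1.2 schedules the awakening samples after "PSG adaptation nights (Baseline 1/ Day -1 and Visit 1/ Day 13) and PSG nights (Baseline 2/ Day 0 and Visit 2/ Day 14". The samples at 3, 6, 9 and 12 hours are taken only at Baseline 1 and Visit 1.
- **Sleep diary.** The endpoint in section 4.2 is "Sleep diary parameters: changes in subjective SE, SOL, WASO, TST, and NWAK compared to baseline", again with no visit named. Section 9.1.9 describes a diary "which they are asked to complete every day starting at Screening Visit (Day -28 to -8) in the evening until End of Trial".

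**The concern.** A last-value rule is harmless where only one value precedes treatment. For the ISI, PSQI, Cold Pressor Test bloods, EEG and attention tests, the last value is the Baseline 1 value. Where a variable is recorded daily, or at both baseline visits, the rule makes a selection, and that selection may disagree with the endpoint definition or with the conditions under which the follow-up value is taken.

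Three things are at stake. The programmer has two stated baselines for one endpoint. The Visit 1 awakening-response change combines a change in night type with time on treatment. The diary covariate is a single entry from an unfamiliar bed, although a run-in of home entries has been collected.

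**Working it through.** No figure in the protocol is specific to this point. The sample size in section 11.1 concerns PSG sleep efficiency and does not depend on the rule. It reproduces: a difference of 6.7 with SD 10 needs 35.96, so 36 per arm or 72 in total, by the two-sample t-test, and 72/0.9 = 80.

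**Daily stress.** Section 4.2 and the synopsis point to Baseline 1 (Day -2 to -1). Section 8.1 schedules a stress assessment at Baseline 2 (Day -1 to 0), so section 11.3 selects that later value. One endpoint has two stated baselines.

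**Saliva.** The rule gives these pairings:

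| Post-treatment sample | Preceding night | Baseline under 11.3 | Night before that baseline |
|---|---|---|---|
| Visit 1 awakening, Day 13 (5 points) | adaptation | Day 0 | second lab night |
| Visit 1 diurnal, Day 13 (4 points) | adaptation | Day -1 | adaptation |
| Visit 2 awakening, Day 14 (5 points) | second lab night | Day 0 | second lab night |

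The last two rows are matched and the first is not. The nine-sample Visit 1 profile therefore has a baseline joined from two unlike days, although a matched Day -1 awakening series exists.

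**Diary, which entry is used.** The nights -2/-1 and -1/0 are both spent in the sleep laboratory. If the Day 0 entry counts, the baseline describes night -1/0. If entries are made in the evening, the last one before randomisation is on Day -1 and describes night -2/-1. Both are laboratory nights.

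**Diary, what is unused.** With Screening on Day -8 there are 8 nights before Day 0, less 2 laboratory nights, leaving 6 at home (-8/-7 to -3/-2). With Screening on Day -28 there are 28 - 2 = 26. Every patient on schedule has at least 6.

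**Diary, illustration of precision.** The inputs here are assumptions and are not in the protocol: night-to-night intraclass correlation (ICC) 0.3 to 0.5, and correlation r between true baseline and true outcome 0.6 to 0.8.

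- Reliability of a k-night mean = k × ICC / (1 + (k - 1) × ICC). For ICC 0.3 / 0.4 / 0.5 this gives 0.30 / 0.40 / 0.50 for k = 1, 0.72 / 0.80 / 0.86 for k = 6 and 0.75 / 0.82 / 0.88 for k = 7.
- Residual variance share = 1 - r² × (baseline reliability) × (outcome reliability).
- Outcome a 7-night home mean, one-entry against six-night baseline: lowest 0.919/0.806 = 1.14 (ICC 0.3, r 0.6), highest 0.720/0.520 = 1.39 (ICC 0.5, r 0.8). As 1 - 1/ratio, this is like losing 12% to 28% of patients.
- Outcome a single home entry: 0.968/0.922 = 1.05 to 0.840/0.726 = 1.16, like losing 5% to 14%.
- With only four baseline entries the ratios are 1.11 to 1.30 (7-night outcome) and 1.04 to 1.13 (single entry).
- Outcome the Visit 2 laboratory-night entry, with r 0.8 for the Baseline 2 laboratory entry and 0.6 for the six-night home mean: 1.02, 1.01 and 0.99 for the three ICCs. There is no gain.

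**The case against.** The strongest reply is that this belongs to the SAP. Section 11.3 lets the SAP modify the plan, section 11.4.2 promises further detail there, and reducing a daily series to an analysis value is ordinary SAP work. That holds for windows and minimum entries. It does not remove the point, because the protocol states a rule, exempts only PSG, and contradicts itself for daily stress.

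On daily stress, the specific wording of section 4.2 could be taken to override the general rule. The item is also the only one in its list without a post-baseline visit, and Baseline 1 and Baseline 2 share Day -1. The conflict is therefore narrow, but no rule of precedence is stated.

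On saliva, section 9.1.2 itself groups the adaptation mornings together and the PSG mornings together, so the authors may well intend the matched pairing. The endpoint wording and section 11.3 do not deliver it. A reader might also infer that the Cold Pressor Test on Day -1 disturbs the Day 0 awakening samples. Nothing in the protocol shows such an effect; the mismatch in night type is enough.

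On the diary, the rule does not say outright that a daily series becomes one entry, and no diary outcome window is set. A Baseline 2 to Visit 2 diary contrast compares two second laboratory nights and is sound. This objection stands: the loss of precision is conditional.

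Actigraphy might seem to suffer in the same way, but section 4.2 gives it no change-from-baseline endpoint, so it is not part of this point.

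**Conclusion.** The rule in section 11.3 is badly fixed for three repeatedly measured secondary variables. The contradiction for daily stress and the saliva mismatch follow from the text and need no assumptions. The diary part rests on a literal reading and matters only if the outcome is taken over home nights. The ratios above illustrate its possible size under assumed correlations and are not estimates for this trial.

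A reader might infer that the treatment comparison or the primary result is compromised. The protocol does not support that. PSG endpoints have their own baseline, matched in night type to Visit 2. All the baseline values precede randomisation and the rule is the same in both arms, so the ANCOVA comparison is not biased. What is affected is the meaning of the within-arm changes, the choice of the daily-stress baseline and possibly precision, all in analyses that section 11.4.2 calls exploratory. The correction is worth making because it is cheap and removes a choice that would otherwise be open at analysis.

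**What to change.** In the SAP, before database lock:

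1. Keep the last-value rule for variables measured once before treatment.
2. State one baseline for daily stress, and say that it replaces the differing wording of sections 4.2 and 11.3.
3. For saliva, pair Visit 1 with Baseline 1 (awakening and diurnal samples) and Visit 2 with Baseline 2 (awakening samples).
4. For the diary and daily stress, use the mean over a fixed window of the last home days before Baseline 1 that all patients have, for example the last 6, with a minimum number of entries such as 4. Pair it with a stated home on-treatment window. The schedule provides 12 home nights on treatment (0/1 to 11/12), up to 14 with the 2-day allowance. A fixed window is better than averaging all run-in nights, whose number varies from 6 to 26.
5. If wanted, keep a separate Baseline 2 to Visit 2 diary contrast beside the PSG results.

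The cost is one more derivation and a rule for the few patients with too few entries. No new data are needed, and section 11.3 allows the SAP to make this change, since the primary endpoint is untouched.

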Abbreviations: AE - Adverse Event, BAI - Beck's Anxiety Inventory (paper PRO), BDI-II - Beck's Depression Inventory revision II (paper PRO), CBC - Complete Blood Count, CPT - Cold Pressor Test, CRP - C-reactive protein, DGSM - Deutsche Gesellschaft für Schlaforschung und Schlafmedizin, DHEA-S - dehydroepiandrosterone sulfate, DSM-5 - Diagnostic and Statistical Manual of Mental Disorders, 5th edition, EDA - Electrodermal Activity, EEG - electroencephalogram, EMAs - Ecological Momentary Assessments (used for daily stress assessment via **AMS-ePRO[®]**), EoT - End of Trial, (e)PRO - (electronic) Patient-Reported Outcome, ESR - Erythrocyte Sedimentation Rate, ESS - Epworth Sleepiness Scale (**AMS-ePRO[®]**), HR - Heart Rate, HRV - Heart Rate Variability, IMP - Investigational Medicinal Product, ISI - Insomnia Severity Index (**AMS-ePRO[®]**), min - minutes, ml - milliliters, PASA - Primary Appraisal Secondary Appraisal (**AMS-ePRO[®]**), PRO - Patient- Reported Outcome, PSG - polysomnography; PSQI - Pittsburgh Sleep Quality Index (paper PRO), PSS-10 - Perceived Stress Scale-10 (paper PRO), rsEEG - resting state electroencephalography, SF-36v2 - Short Form-36 version 2.0 (paper PRO), SSQ-25 - Subclinical Stress Symptom Questionnaire-25 (paper PRO), TAP - Test of Attentional Performance, WEIMuS - Würzburg Fatigue Inventory (paper PRO).

[^]Visit 1 may be performed on Day 12 +2 days. In any case, Visit 1 and Visit 2 will be performed on two consecutive days.

^{^^}Follow-up Visit may be performed on Day 28 +3 days.

◦ Demographics include sex, height and weight.

* Starting IMP treatment after having performed all Baseline 2 assessments and after randomization at midday Day 0 for 14 consecutive days (+ maximum 2 days allowance) until Visit 2 (Day 13).

◦◦ Sleep diary will be completed daily; starting at Screening Visit until End of Trial

Stress biomarkers in saliva: cortisol, alpha-amylase, dehydroepiandrosterone sulfate (DHEA-S) at 5 time points: after awakening from PSG nights at Baseline 1/ Day -1, Baseline 2/ Day 0, Visit 1/ Day 13 and Visit 2/ Day 14 collection of around 0.5 to 1 ml saliva at 0 minutes, 15 minutes, 30 minutes, 45 minutes, 60 minutes (5 time points) for the assessment of Cortisol Awakening Response (CAR) and additionally at Baseline 1/ Day -1 and Visit 1/ Day 13 diurnal profile of stress biomarkers by collecting saliva samples at 3-hourly intervals over 12 hours (4 time points) synchronized to the awakening time.

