11.4.2 Secondary Efficacy

For all secondary variables, exploratory statistics comparing the 2 treatment groups will be performed. Difference from baseline will be used, as appropriate. Group comparisons of continuous numeric parameters will be tested using an ANCOVA including treatment, the stratification factor sex, and the baseline value of continuous numeric parameters as covariate; comparisons of dichotomous variables are specified by using the Fisher's Exact Test.

Secondary analyses on efficacy will be exploratory in nature without adjustment for multiplicity. All secondary analyses will be performed with two-sided hypotheses on superiority using a Type I error level of 5%.

Secondary efficacy variables are the following:

Polysomnography at Baseline 2 and Visit 2

- SOL
- WASO
- TST
- NWAK
- Latencies to S1, S2, S3, REM
- Arousal Index (Arl).

Biochemical parameters

- Resting state cortisol and other stress-related parameters in saliva
- Serum cortisol levels and other stress-related parameters in response to the stress induction by CPT
- Stress test induced inflammation parameters in blood serum.

Actigraphy

- Continuous in-home assessment of sleep
- Daytime activity.

Patient Questionnaires

- Subclinical Stress Symptom Questionnaire-25 (SSQ-25)
- Primary Appraisal Secondary Appraisal (PASA)
- Perceived Stress Scale-10 (PSS-10)
- Epworth Sleepiness Scale (ESS)
- Würzburg Fatigue Inventory (WEIMuS)
- Short Form-36 (SF-36v2)
- Insomnia Severity Index (ISI)
- Pittsburgh Sleep Quality Index (PSQI)
- Beck's Depression Inventory-II (BDI-II)
- Beck's Anxiety Inventory (BAI).

Sleep diary (adapted from DGSM) data: subjective SE, SOL, WASO, TST, NWAK

Continuous digital stress assessments

Neurexan® response

Exploratory Efficacy Variables

- EEG based vigilance fluctuations during resting state
- EEG based vigilance fluctuations during CPT
- EEG based asymmetry index during resting state
- EEG based vigilance fluctuations during CPT
- Regional changes in spectral characteristics of EEG during resting state
- Regional changes in spectral characteristics of EEG during CPT
- Cognitive performance in three attentional tasks

- PSG sleep parameters derived from the two adaptation nights at Baseline 1 and Visit 1.

Correlations between

- Changes in sleep parameters, stress parameters, and daytime performance
- Changes in sleep parameters, stress parameters, and inflammatory parameters

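### Responder status is an outcome observed after randomisation, yet the protocol lists it as a subgroup alongside baseline factors

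*Protocol*

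**What the plan says.** Section 11.3, under Subgroup Analyses, introduces one list with "The following subgroups will be defined". Its entries are age, sex, "Neurexan® responder vs. non-responder", duration of insomnia split at one month, and cortisol response as influenced by hormonal contraceptives. The synopsis (2.1) repeats the list. Neither place separates factors known at baseline from those observed later.

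On timing, section 11.2 states that "allocation to treatment will take place after completion of all baseline assessments prior to beginning of trial treatment". The footnote to the schedule in section 2.2 reads "Starting IMP treatment after having performed all Baseline 2 assessments and after randomization at midday Day 0". The schedule shows no trial medication during the run-in.

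Section 11.4.2 lists "Neurexan® response" among the secondary efficacy variables and says "For all secondary variables, exploratory statistics comparing the 2 treatment groups will be performed". It names ANCOVA (treatment, sex, baseline value) for continuous variables and Fisher's exact test for dichotomous ones. Secondary analyses are exploratory and not adjusted for multiplicity.

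The protocol does not define a responder. It does not say whether placebo patients can be responders, or which contrast the subgroup is meant to serve.

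**The concern.** A subgroup analysis of a treatment effect is sound only if membership is fixed before treatment, so that the arms remain comparable within each subgroup. Response is produced partly by treatment and partly by the patient's own course. Selecting on it leaves arms that differ in that course.

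The direction of the bias depends on the contrast:

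- **Same criterion in both arms.** If the drug works, some Neurexan patients reach the criterion with its help, while placebo responders reach it through a favourable course alone. Neurexan responders then have the poorer underlying course, and an endpoint the drug does not touch tends to look worse on Neurexan.
- **Neurexan responders against all placebo patients.** Only one arm is selected for doing well, so an unaffected endpoint tends to look better on Neurexan.

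At stake is a spurious exploratory finding, or a real effect that appears smaller than it is.

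**Working it through.** **1. Can response be known before randomisation?** By sections 11.2 and 2.2 the order is baseline assessments, allocation on Day 0, then first intake. With no active run-in, no response to trial medication exists before allocation. Section 11.4.2 treats response as an efficacy variable. The same variable is therefore both an outcome and a subgroup factor.

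**2. Planning figures (section 11.1).** SD 10, difference 6.7, two-sided 5%, power 80%, 72 patients. The standardised effect is 6.7/10 = 0.67. The two-sample t-test gives 35.96, so 36 per arm and 72 in total, with power 0.8005; 72/0.9 = 80. The stated figures reproduce and are not disputed.

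**3. Assumptions, because the protocol gives none.** The SD of the change in sleep efficiency (SE) equals 10. A responder is a patient whose SE change exceeds a fixed cut-off. The second endpoint has correlation r with SE change and no treatment effect.

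**4. Effect on the SE comparison itself.** Let a = (c − μ)/10 for cut-off c and arm mean μ (6.7 on Neurexan, 0 on placebo). With φ and Φ the standard normal density and distribution function:

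- mean SE change in responders = μ + 10·φ(a)/(1 − Φ(a))
- mean SE change in non-responders = μ − 10·φ(a)/Φ(a)

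At c = 5:

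- Neurexan: a = −0.17, response rate 0.567, responder mean 6.7 + 6.93 = 13.63, non-responder mean 6.7 − 9.09 = −2.39.
- Placebo: a = 0.50, response rate 0.309, responder mean 11.41, non-responder mean −5.09.
- Difference in responders: 13.63 − 11.41 = 2.22. In non-responders: −2.39 − (−5.09) = 2.70.

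The true effect is 6.7 points in every patient. For cut-offs from 0 to 10 points the apparent effect is 1.6 to 3.0 points in responders and 2.0 to 3.6 in non-responders.

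**5. Effect on an unaffected endpoint, same criterion in both arms.** The spurious difference in responders, in SD units of the endpoint, is r·(λN − λP), with λ = φ(a)/(1 − Φ(a)) for each arm.

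| Criterion met by | Expected responders, Neurexan vs placebo | λN − λP | r = 0.3 | r = 0.5 | r = 0.7 | r = 0.8 |
|---|---|---|---|---|---|---|
| one third of placebo | 21 vs 12 | 0.652 − 1.091 = −0.439 | −0.13 | −0.22 | −0.31 | −0.35 |
| one half of placebo | 27 vs 18 | 0.426 − 0.798 = −0.372 | −0.11 | −0.19 | −0.26 | −0.30 |

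False-positive rates by simulation (36 per arm, 6,000 trials per setting, ANCOVA with treatment, sex and baseline within responders):

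| SE shift 0.67 SD | r = 0.3 | r = 0.5 | r = 0.7 | r = 0.8 |
|---|---|---|---|---|
| one third of placebo | 6.2% | 9.7% | 15.5% | 22.6% |
| one half of placebo | 6.0% | 9.6% | 15.8% | 19.8% |

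The same ANCOVA in all patients rejects in 4.4–5.2%. With no drug effect on SE, the responder analysis rejects in 5.0–5.5%, so there is no inflation.

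**6. Neurexan responders against all placebo, no drug effect.** The spurious difference is r·λP: 0.3 × 1.091 = 0.33 and 0.5 × 1.091 = 0.55 SD (one third), or 0.3 × 0.798 = 0.24 and 0.5 × 0.798 = 0.40 SD (one half), all favouring Neurexan. Simulated two-sided t-test rejection rates (20,000 trials per setting) are 15.5% and 37.1% (one third) and 12.8% and 27.7% (one half), for r = 0.3 and 0.5 respectively. The nominal level is 5%.

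**The case against.** The best reply is that the protocol does not plan the analysis being criticised. It says only that subgroups will be defined and gives no model for them. The label can be read as a split of the Neurexan arm into two kinds of patient, which would be an associational profile and not a treatment effect. The list also contains the item on cortisol response and contraceptives, so it is not strictly a list of treatment-effect strata. Definitions and contrasts normally belong in the SAP. Everything concerned is exploratory.

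Much of this stands. The contrast is unstated, so the error rates illustrate plausible uses and are not properties of a written analysis. The Neurexan-responders-against-all-placebo contrast appears nowhere in the protocol. The figures at r = 0.7 and 0.8 are the least realistic. The endpoints most closely tied to SE are ones such as total sleep time and wake after sleep onset, and a drug that shifts SE by 0.67 SD would hardly leave those unchanged. At r = 0.3 with a common criterion the inflation is about one percentage point.

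It does not remove the point. The missing definition is not the complaint: no later definition turns an observed outcome into a baseline factor. A split of the Neurexan arm alone is also non-randomised and selected on outcome, and nothing in section 11.3 confines the item to descriptive use. The exploratory label deals with multiplicity and does nothing about selection bias.

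**Conclusion.** The concern holds. Responder status cannot serve as a subgroup for a treatment effect in this trial, and its place in the lists in sections 2.1 and 11.3 is a defect in what the protocol fixes.

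Its size depends on the contrast. With a common criterion and the planned drug effect, the false-positive rate for an unaffected endpoint is about 6% to 10% at r of 0.3 to 0.5, with higher figures only at correlations that are less plausible for such an endpoint. With Neurexan responders against all placebo patients it is about 13% to 37% over the same range of r, even when the drug has no effect. A real SE effect of 6.7 points would shrink to between 1.6 and 3.6 points within the responder strata.

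These figures rest on normal data, an SE-based criterion, the assumed cut-offs and correlations, and an SD of change equal to the stated 10. The primary ANCOVA and the sample size are not affected, so this should be corrected but does not endanger the main result.

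**What to change.** Delete the responder item from the subgroup lists in sections 2.1 and 11.3. Keep treatment response as a secondary outcome only, with one criterion fixed before unblinding and applied identically in both arms. Compare the proportions between all randomised patients with the Fisher's exact test already provided for in section 11.4.2. If responder profiles are wanted, show them by arm, label them descriptive and non-randomised, and do not present them as treatment effects.

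The cost is a change of wording in the protocol and SAP, and the loss of one exploratory contrast. No data collection, sample size or primary analysis changes.
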